4.1.3.3 EXACT CONDITIONAL LOGISTIC REGRESSION

The primary endpoint, sustained platelet count, is also tested by means of a 2-sided exact test (using exact conditional logistic regression⁶), stratified for the stratification factors (history of splenectomy and receiving concurrent ITP therapies at baseline) and using the baseline platelet count (continuous) and randomized treatment as fixed covariates, at the 2-sided 5% significance level, in the chronic ITP population. A maximum exact conditional likelihood estimate of the OR will be obtained, using the Newton-Raphson algorithm. In the event the algorithm does not converge, the median unbiased estimate will be used⁵. A likelihood ratio test will be conducted to test the null hypothesis that the log OR is equal to zero against the alternative that it is different from zero.⁷ In case of empty cells for all strata within one treatment, a Firth regression will be used¹⁸. The treatment effect will be presented as the OR (by exponentiating the log OR) together with its 95% confidence interval (CI) and 2-sided p-value. An OR of more than 1 represents a higher response rate for efgartigimod compared to placebo.

Missing data due to a reason of one of the main intercurrent events as described above (see section 4.1.2.1) will be analyzed as a non-responder (composite variable strategy). Missing data for other reasons will be imputed as described in section 4.1.2.5, approach 1.

4.1.3.4 STRATIFIED MANN-WHITNEY TEST.

The extent of disease control, the number of bleeding events (WHO bleeding scale ≥ 1) and the number of significant bleeding events (WHO bleeding scale ≥ 2) are tested by means of a Wilcoxon-Mann-Whitney test stratified for the stratification factors (history of splenectomy and receiving concurrent ITP therapies at baseline) and baseline platelet count category ($<15 \times 10^9/L$ versus $\geq 15 \times 10^9/L$) included as independent variable. An estimate of the location shift will be provided (Hodges-Lehmann estimator of the treatment difference), along with the associated 95% CI and 2-sided p-value. The 2-sided p-value resulting from this hypothesis test will inform on whether the null hypothesis that the distributions of number of cumulative weeks for both treatment groups are identical can be rejected. The stratified Mann-Whitney test for extent of disease control will be done for both the chronic ITP population and the overall population.

Missing bleeding assessments strictly after of one of the main intercurrent events will not be imputed. For ‘increase of dose and/or frequency of concurrent ITP therapies or start of a new concurrent ITP therapy’ and ‘initiation of rescue therapy’ the whole treatment period should be taken into account. In case of rescue therapy, the bleeding events will not be imputed for 4 weeks strictly after the initiation of the therapy (the

	Statistical Analysis Plan	
ARGX-113-2004	Final analysis	Final 1.0 of 7NOV2023

initiation of the therapy is the start date/time of the administration of the first rescue treatment for that occurrence).

Missing bleeding assessments for other reasons than the main intercurrent events will be imputed as described in section 4.1.2.5 (approach 3).

4.1.3.5 *MIXED MODEL FOR REPEATED MEASUREMENTS*

For changes from baseline (see section 4.1.2.3), between treatment group differences will be analyzed by means of Mixed Models for Repeated Measurements (MMRM). All available data will be included. Non-missing values after one of the main intercurrent events will be imputed with the baseline value/score. Other (missing) values will not be imputed. The model will include treatment, analysis visit and treatment by visit interaction terms as fixed effects, with baseline value, baseline by visit interaction, and stratification factors as covariates. Only analysis visits within the treatment phase will be considered. Within-participant correlation will be modeled by assuming an unstructured covariance matrix for the error terms and Kenward-Roger degrees of freedom method will be used. Least square (LS) means for placebo and efgartigimod will be reported, along with the difference in LS means, 95% 2-sided CI, and 2-sided p-value. If the default Newton–Raphson algorithm used by SAS PROC MIXED fails to converge, the following steps will be taken to avoid lack of convergence while maintaining an unstructured variance:

- The Fisher scoring algorithm (via the SCORING=5 option of the PROC MIXED statement) will be used to obtain the initial values of covariance parameters.
- If the above fails, the no-diagonal factor analytic structure will be used, which effectively performs the Cholesky decomposition via the TYPE=FA0(V) option of the REPEATED statement, where V is the total number of distinct visits in the response vector (counting only rows where all model components are non-missing).
- If all of the above fail, the variance-and-correlations parameterization will be attempted using TYPE=UNR.

In the rare case where all of the above steps fail, the following covariance structures will be tested for convergence (in order): ANTE(1), TOEPH, ARH(1), CSH, TOEP, AR(1), and CS. However, if one of these simpler covariance structures is used, this needs to be implemented in combination with sandwich variance estimator (EMPIRICAL option).

This model will be applied for the mean changes in platelet count levels, PRO (FACIT-Fatigue, FACT-Th6) and QoL (SF-36: 8 subdomain scores, P-CS and M-CS; ITP-PAQ: 9 (for male) or 11 (for female) scales).

4.1.3.6 *COX PROPORTIONAL HAZARDS REGRESSION*

The Cox proportional hazard model will be used to calculate the estimate of the hazard ratio (HR) and 95% confidence interval for the treatment effect of the extent of disease control as complementary analysis for the first key secondary endpoint (see section 4.1.2.2), and the time to platelet count response (see section 4.1.2.3).

The model will include treatment as fixed effects, with baseline platelet level and stratification factors as covariates. The HR for efgartigimod PH20 SC vs. placebo

	Statistical Analysis Plan	
ARGX-113-2004	Final analysis	Final 1.0 of 7NOV2023

PH20 SC will be provided, along with the associated 95% 2-sided Wald-type CI and 2-sided p-value.

4.1.4 *Subgroup analyses for efficacy*

Subgroups are defined based on the following categorizing factors:

- Fixed dosing regimen (weekly versus bi-weekly): as derived in section 3.6.2
- Recruitment cohort (wave 1 versus wave 2): as derived in section 3.3.2
- History of splenectomy (yes versus no)
- Receiving concurrent ITP therapies at baseline (yes versus no)
- Baseline platelet count: ($<15 \times 10^9/L$, $\geq 15 \times 10^9/L$)
- Time since diagnosis (chronic versus persistent)
- Number of prior ITP therapies (<3 prior therapies, ≥ 3 prior therapies)
- Sex at birth (male, female)
- Region (East Asia / Europe / LATAM / MEA / non-EU CEE / North America / rest of the world): as defined in section 3.3.2
- Age category (18- <65 years; 65- <75 years; ≥ 75 years)
- Race (Asian, Black or African American, White, Other)
- Weight category at baseline (<50 kg, 50- <75 kg, 75 – <100 kg, 100 – <125 kg, ≥ 125 kg)
- Prior Rituximab (yes versus no): as defined in section 3.5.2
- Prior TPO-RA (yes versus no): as defined in section 3.5.2

Note that subgroup categories with less than 5 participants (overall) will not be included in the tables. For region, North America will always be shown. Other regions with less than 15 participants (overall) will be shown in the 'rest of the world' subgroup.

Subgroup analyses will be performed on the following efficacy endpoints:

- Sustained platelet count response (week 19 – 24) in the overall population
- Sustained platelet count response (week 19 – 24) in the ITP chronic population (recruitment cohort only)
- Extent of disease control (first key secondary endpoint) in the overall population (all subgroup analyses except fixed dosing regimen [weekly versus bi-weekly]).

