9.3. Sample Size Determination

Approximately 180 participants with chronic ITP and up to 39 participants with persistent ITP will be randomized in a 2:1 ratio to receive efgartigimod PH20 SC or placebo PH20 SC, respectively.

The null and alternative hypotheses are defined as $H_0: \pi_1 = \pi_2$ vs $H_A: \pi_1 \neq \pi_2$, where π_1 and π_2 are the population probabilities to achieve a sustained platelet count response (primary efficacy endpoint) for participants with chronic ITP receiving placebo PH20 SC and for participants with chronic ITP receiving efgartigimod PH20 SC, respectively.

In the placebo PH20 SC group, the response rate of participants with chronic ITP who reach the primary endpoint is expected to be $\leq 5\%$, while the response rate of participants with chronic ITP in the efgartigimod PH20 SC group is expected to be 21.8% (ie, $\pi_1=0.05$ and $\pi_2=0.218$), based on the observed response rates in trial ARGX-113-1801. Given these assumptions, a total of $N=180$ randomized participants with chronic ITP will ensure a power of at least 80% to reject the null hypothesis at a 1-sided significance level α of 0.025, based on Fisher’s exact test.

For the first key secondary endpoint “extent of disease control,” assuming distributions for cumulative number of weeks of disease control over the planned 24-week treatment period with platelet counts of $\geq 50 \times 10^9/L$ in the chronic ITP population similar to those observed in ARGX-113-1801, a total of $N=180$ participants will ensure a power of $>99\%$ (2-sided α of 0.05), conditionally on reaching the primary endpoint, to detect a significant difference between both treatment groups. For ensuring a power of at least 90%, a total number of $N=75$ participants would be needed, given these assumptions. Calculations are based on the Wilcoxon-Mann-Whitney test, where the O’Brien-Castelloe approach¹⁴ was taken to compute the power, taking into account a 2:1 allocation ratio to receive efgartigimod PH20 SC versus placebo PH20 SC.

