9.5.5.5. Complementary Analyses

To facilitate interpretation of the estimated treatment effect in the primary analysis, complementary analyses will be conducted where the main intercurrent events are handled differently, eg, by using the “treatment policy” strategy. Furthermore, an exact logistic regression analysis, in which the continuous baseline platelet count level is added as covariate instead of the baseline platelet count category, will be conducted as supportive analysis. Details will be provided in the SAP.

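### The supportive exact regression of the primary endpoint names a likelihood ratio test without an exact reference distribution, so its single p-value may not be exact and can be significant where the exact test is not

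*SAP*

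**What the plan says.** Protocol 9.5.5.5 commits to "an exact logistic regression analysis, in which the continuous baseline platelet count level is added as covariate", as a supportive analysis to the stratified CMH test.

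SAP 4.1.3.3 carries this out. The primary endpoint "is also tested by means of a 2-sided exact test", by exact conditional logistic regression, "at the 2-sided 5% significance level, in the chronic ITP population". The odds ratio is to be the conditional maximum likelihood estimate, or the median unbiased estimate if the algorithm fails to converge. The section then names a test: "A likelihood ratio test will be conducted to test the null hypothesis that the log OR is equal to zero". The next sentence adds an exception: "In case of empty cells for all strata within one treatment, a Firth regression will be used". One odds ratio, one confidence interval and one 2-sided p-value are to be presented, in Table 14.2.1.3.

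The section does not say whether the p-value is the exact one or the likelihood ratio one, which reference distribution the likelihood ratio statistic takes, or which test goes with Firth regression. The code in SAP 9.1.2 is redacted. That is not a fault of the plan, but it means the readable text has to settle the matter, and it does not.

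**The concern.** An exact test takes its p-value from the conditional distribution of the data given the margins, so its level is guaranteed whatever the counts. A likelihood ratio test is normally referred to chi-square with 1 degree of freedom, which is a large-sample approximation. The two can fall on opposite sides of 0.05 when responders are few, and the protocol expects a placebo rate of at most 5%, about 3 of 60.

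The analysis is there to support the CMH result with a method that does not rely on large-sample theory. If its p-value comes from chi-square, it can appear to confirm the primary result when the test it is labelled as would not. Two programmers following the same paragraph could also report different p-values.

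**Working it through.** **Inputs.** Protocol 9.3: 180 participants with chronic ITP at 2:1, so 60 placebo and 120 efgartigimod; rates 5% and 21.8%. Expected responders are 60 × 0.05 = 3 and 120 × 0.218 = 26.2. The pooled rate is (3 + 26.16)/180 = 16.2%. SAP 4.1.3.3: two-sided 5% level. The alternative rate of 15% is my assumption, to show a smaller effect. The enumeration uses a single 2×2 table without strata or the platelet covariate.

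**The plan's own figure.** Full enumeration of the two binomials with Fisher's exact test at one-sided 0.025 gives 85.2% power. The stated figure of at least 80% holds.

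**Likelihood ratio test.** With x of 60 and y of 120 responders, G = 2[f(x,60) + f(y,120) − f(x+y,180)], where f(a,n) = a·ln(a/n) + (n−a)·ln((n−a)/n). For 3 versus 19: f(3,60) = −11.911, f(19,120) = −52.427, f(22,180) = −66.839. So G = 2 × 2.501 = 5.00, and chi-square on 1 df gives p = 0.025.

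**Exact test.** Given 22 responders in total, the efgartigimod count is hypergeometric (180, 120, 22). Summing the probabilities of all outcomes no more likely than 19 gives p = 0.051.

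Other tables with responders in both arms:

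| Placebo /60 | Efgartigimod /120 | Likelihood ratio p | Exact p |
|---|---|---|---|
| 1 | 11 | 0.034 | 0.064 |
| 2 | 15 | 0.032 | 0.058 |
| 3 | 19 | 0.025 | 0.051 |
| 4 | 21 | 0.037 | 0.066 |
| 5 | 24 | 0.035 | 0.053 |

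The conditional-likelihood version gives nearly the same values (0.026 for 3 versus 19).

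**How often they disagree.** The probability that the likelihood ratio test is significant and the exact test is not:

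- 5% versus 21.8%: 4.4%. This equals the difference in power, 91.3% − 86.9%, because no table disagreed the other way.
- 5% versus 15%: 13.0%.

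Leaving out every table with an empty arm does not change either figure to the first decimal.

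**Type I error at two-sided 0.05, equal rates in both arms.** Firth regression is represented by adding one half to each cell. The two middle columns apply the SAP rule, with Firth used when one arm has no responders.

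| Common rate | Likelihood ratio on every table | SAP rule, Firth penalised likelihood ratio | SAP rule, Firth Wald | Fisher |
|---|---|---|---|---|
| 2% | 6.7% | 2.1% | 1.2% | 2.0% |
| 3% | 8.0% | 3.0% | 2.2% | 2.6% |
| 5% | 6.7% | 4.5% | 3.3% | 3.0% |
| 10% | 5.7% | 5.7% | 5.6% | 3.4% |
| 16.2% | 5.3% | 5.3% | 5.3% | 3.7% |

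Over all rates, the maximum is 8.0% for the likelihood ratio test on every table, about 5.7% for the SAP rule and 4.2% for Fisher. A likelihood ratio statistic referred to its exact conditional distribution also stays at or below 4.2%.

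**Stratified check.** A simulation with four strata (assumed shares 25/12/40/23%) and a continuous baseline count gave 6.9% at a 5% rate with empty-arm tables kept in the likelihood ratio test. It gave 3.9% when those tables were not counted as rejections.

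**The case against.** A reader might infer that this analysis rejects too often just where exact methods are needed, with error of 6.7% to 8.0% at response rates of 2% to 5%. The documents do not support that. Those figures apply the likelihood ratio test to tables with no responder in an arm, and SAP 4.1.3.3 sends such tables to Firth regression. With 0 versus 5 responders, for example, the likelihood ratio p is 0.042, but the SAP would report a Firth result: 0.14 by penalised likelihood ratio or 0.24 by Wald, against 0.17 exact. Under the written rule the test is conservative at low rates.

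A reader might also infer that the SAP plainly takes its p-value from chi-square. It does not say so. It names an exact test as well, and a likelihood ratio statistic with an exact reference would hold its level. The redacted code may resolve the question.

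Finally, the analysis is supportive and lies outside the fixed testing sequence, so the trial's type I error is not at stake.

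All three points stand, and they reduce the matter to one of specification. They do not remove it. Firth regression leaves the disagreements among tables with responders in both arms untouched, and it is not exact either. Its unnamed test also matters: with 0 versus 10 responders the penalised likelihood ratio p is 0.016, the Wald p is 0.094 and the exact p is 0.032.

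**Conclusion.** The point holds as a gap between label and method. SAP 4.1.3.3 promises an exact test, names a likelihood ratio test with no exact reference, and reports one p-value. If the usual chi-square reference is used, the result can be significant where the exact test is not, with responders in both arms. The probability is about 4.4% at the planned rates and 13% at 5% versus 15%. Among tables that do not go to Firth regression, the disagreement ran only towards apparent support in every scenario checked.

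The excess over the 5% level is small, at most about 0.7 points near a 10% common rate, taking Firth by penalised likelihood ratio. The CMH test and the testing hierarchy are unaffected, so this is a minor point that is worth correcting.

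The sizes rest on unstratified 60 versus 120 tables without the covariate, on a chi-square reference the SAP does not state, and on reading the Firth rule as applying when one arm has no responders. Conditioning on strata and a continuous platelet count makes the exact reference set sparser, so the exact p-values in the trial will differ from those shown.

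**What to change.** In SAP 4.1.3.3:

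- State that the reported p-value and confidence interval come from the exact conditional distribution, and name the test (exact conditional score or probability test).
- Delete the likelihood ratio sentence, or keep the test as an additional result labelled asymptotic.
- Keep the median unbiased estimate for when the conditional maximum does not exist.
- Where one arm has no responders, take the p-value from the same exact test. If Firth regression is retained there, name its test (penalised likelihood ratio or Wald) and label it non-exact.

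The change takes a few sentences and needs no new data. The cost is a somewhat less favourable supportive p-value: at the planned rates, unstratified, the chance of p < 0.05 is 86.9% with the exact test against 91.3% with the chi-square likelihood ratio test. Conditioning on the platelet covariate could lower the exact figure further.

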4.2 PHARMACOKINETICS

4.2.1 *Available data*

Blood samples will be collected for the determination of efgartigimod concentration at the time points indicated in the schedule of assessments (see section 9.5).

All PK samples are to be collected predose, on the day of IMP administration.

All concentration data-points with deviations outside these permitted ranges will be excluded from the descriptive statistics on concentrations by scheduled timepoint, and a remark will be added in the appropriate listing.

	Statistical Analysis Plan	
ARGX-113-2004	Final analysis	Final 1.0 of 7NOV2023

The PK samples taken after a missed dose up to the next administered dose will be excluded from descriptive statistics, a remark will be added in the appropriate listing.

4.2.2 Derivation rules

Not applicable

4.2.3 Presentation of results

For tables by fixed dosing regimen, only visits of the fixed dosing schedule period (ie, baseline up to week 3 and week 16 up to week 24) will be tabulated. In this first period of baseline up to week 3, all participants have weekly dosing per protocol. For the second period, the fixed dosing regimen is defined as explained in section 3.6.2.

Individual concentration data and actual blood sampling times from start of injection for PK assessments will be listed. Data issues like time deviations will be mentioned in the remarks.

Descriptive statistics on concentration data will be presented in tables per visit (and fixed dosing regimen (weekly or every other week)). A similar table will be created by ADA and NAb against efgartigimod, and antibodies against rHuPH20 Participant Classification.

